5.3 Agent Administration

5.3.1 Pegylated Liposomal Doxorubicin (PLD):

5.3.1.1 Administration

PLD is administered intravenously, and the first dose of PLD should be administered at a range of 1 mg per minute as per the FDA package insert. If no infusion reactions occur, the infusion rate can be increased to complete the administration of the drug over one hour. The infusion line should not be rapidly flushed.

5.3.1.2 Dosing

The dose used in this study will be 40 mg/m² IV once every 4 weeks. The drug may be administered ± 3 days from the scheduled next infusion because of vacations, weather, holidays, etc. The dose should be calculated using the weight and height on the day of infusion, and actual body weight should be used as per the package insert.

5.3.1.3 Drug, Tubing and Filtration

PLD should not be used with in-line filters. Please see the PLD package insert for additional details, and PLD should be administered per the FDA package insert and institutional policies.

5.3.1.4 Hydration

There is no required hydration. Any hydration will be determined by the treating investigator.

5.3.1.5 Special Equipment

No special equipment is needed for PLD infusion.

5.3.1.6 Observation period

There is no stated length of observation for PLD, and should be determined by the treating investigator.

5.3.1.7 Infusion Reactions

Infusion reactions are described with PLD. The PLD package insert and standard institutional policy should be followed for management of these reactions. Desensitization procedures are permitted in participants who experience an allergic reaction to PLD. Patients who have an allergic reaction to PLD are allowed to continue on the protocol after a discussion with the Overall PI and a consultation with allergy. A desensitization procedure administers the total planned dose of PLD over a longer period of time under the guidance of the Investigator and Allergist. The duration of the infusion of PLD may vary with each patient's specific symptoms.

5.3.1.8 Order of Administration

If PLD and pembrolizumab infusions do occur on the same day, pembrolizumab should be given first, followed by PLD.

5.3.1.9 Caregiver Precautions

There are no specific caregiver precautions. Patients may develop, after PLD infusion, a reddish-orange color to their urine and other body fluids. This non-toxic reaction is due to the color of the PLD product and will dissipate as the drug is eliminated.

5.3.2 **Pembrolizumab:**

5.3.2.1 Administration and Dosing

Pembrolizumab 200 mg will be administered as a 30 minute IV infusion every 3 weeks. The drug may be administered ± 3 days from the scheduled next infusion because of vacations, weather, holidays, etc. Sites should make every effort to target infusion timing to be as close to 30 minutes as possible. However, given the variability of infusion pumps from site to site, a window of -5 minutes and +10 minutes is permitted (i.e., infusion time is 30 minutes: -5 min/+10 min).

5.3.2.2 Drug, Tubing and Filtration

No special IV tubing and/or filtration are necessary.

5.3.2.3 Hydration

There is no required hydration. Any hydration will be determined by the treating investigator as clinically indicated.

5.3.2.4 Observation period

Per package insert for pembrolizumab.

5.3.2.5 Protocol specific procedures

Vital signs should be taken as per institutional policy.

5.3.2.6 Infusion Reactions

Infusion reactions are described with pembrolizumab. Please see section 6.3. Desensitization procedures are permitted in participants who experience an allergic reaction to pembrolizumab. Patients who have an allergic reaction to pembrolizumab are allowed to continue on the protocol after a discussion with the Overall PI and a consultation with allergy. A desensitization

procedure administers the total planned dose of pembrolizimab over a longer period of time under the guidance of the Investigator and Allergist. The duration of the infusion of pembrolizumab may vary with each patient's specific symptoms.

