5.6 Criteria for Taking a Participant Off Protocol Therapy

Duration of therapy will depend on individual response, evidence of disease progression and tolerance. In the absence of treatment delays due to adverse event(s), treatment may continue until one of the following criteria applies:

- Disease progression
- Intercurrent illness that prevents further administration of treatment
- Unacceptable adverse event(s)
- Participant decides to withdraw from the protocol therapy
- General or specific changes in the participant's condition render the participant unacceptable for further treatment in the judgment of the treating investigator
- Participant has completed 35 treatments (approximately 2 years) with pembrolizumab (Note: participant may continue on study receiving only PLD at the discretion of the treating investigator)

Participants will be removed from the protocol therapy when any of these criteria apply. The reason for removal from protocol therapy, and the date the participant was removed, must be documented in the case report form (CRF). Alternative care options will be discussed with the participant.

Regarding length of duration of treatment of PLD, investigator should follow the FDA package insert for PLD.

Before participants continue on PLD for more than 8 cycles, the treating physician must confer with the Overall PI and obtain approval to do so.

If participants are removed from PLD therapy because of PLD toxicities, they are tolerating Pembrolizumab, and there is no evidence of RECIST progression, participants may continue on Pembrolizumab alone after discussion and approval from the Overall PI.

For Centralized Subject Registrations, the research team submits a completed Off Treatment/Off Study form to ODQ when a participant comes off study. This form can be found on the ODQ website or obtained from the ODQ registration staff. Other investigative sites will inform the Project Manager as soon as a participant is taken off protocol therapy. The Project Manager will then make the relevant updates in OnCore.

For Decentralized Subject Registrations, the research team updates the relevant Off Treatment/Off Study information in OnCore.

In the event of unusual or life-threatening complications, treating investigators must immediately notify the Overall PI,

- [name]. at [contact].

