6. DOSING DELAYS/DOSE MODIFICATIONS

Investigators should assess toxicities and make a determination which agent(s) is responsible for the toxicity and grade the toxicity. Dose delays and modifications will be made as indicated in the following table(s). The descriptions and grading scales found in the revised NCI Common Terminology Criteria for Adverse Events (CTCAE) version 4.0 will be utilized for dose delays and dose modifications. A copy of the CTCAE version 4.0 can be downloaded from the CTEP website

http://ctep.cancer.gov/protocolDevelopment/electronic_applications/ctc.htm.

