Grade 2: Painful erythema, edema or ulcers but can eat.	
 • Delay dosing up to 2 weeks or until resolved to grade 0 or 1. • Discontinue doxil if no resolution after 2 weeks. • If resolved to grade 0 or 1 within 2 weeks: 
and no previous grade 3 or 4 HFS, continue treatment at previous dose
 
or
 
And previous Grade 3 or 4 toxicity; decrease dose by 25%

Grade 3: Painful erythema, edema or ulcers and cannot eat.	
 • Delay dosing up to 2 weeks or until resolved to grade 0 or 1. Decrease dose by 25% and return to original dose interval • Discontinue doxil if no resolution after 2 weeks
Grade 4: Diffuse or local process causing infectious complications, or a bed ridden state or	
 • Delay dosing up to 2 weeks or until resolved to grade 0 or 1, then decrease dose by 25% and

hospitalization.	
 return to original dose interval • Discontinue doxil if no resolution after 2 weeks
------------------	--

Neutropenia and Thrombocytopenia

Toxicity	Dose Adjustment
Neutropenia and Thrombocytopenia	
Grade 1	No dose reduction
Grade 2	Delay until ANC \geq 1500 and plts \geq 100,000; resume treatment at previous dose
Grade 3	Delay until ANC \geq 1500 and plts \geq 100,000; resume treatment at previous dose
Grade 4	Delay until ANC \geq 1500 and plts \geq 100,000; resume at 25% dose reduction or continue previous dose with prophylactic granulocyte growth factor.

6.2 Dose Modifications for Pembrolizumab:

Adverse events (both non-serious and serious) associated with pembrolizumab exposure may represent an immunologic etiology. These adverse events may occur shortly after the first dose or several months after the last dose of treatment. Pembrolizumab must be withheld for drug-related toxicities and severe or life-threatening AEs as per Table 3 below. See Section 6.3.1 and Events of Clinical Interest Guidance Document for supportive care guidelines (**Appendix B**), including use of corticosteroids.

Table 3

Dose Modification Guidelines for Drug-Related Adverse Events (Please also see Appendix B)

Toxicity	Hold Treatment For Grade	Timing for Restarting Treatment	Discontinue Participant

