Note: Permanently discontinue for any severe or Grade 3 drug-related AE that recurs or any life-threatening event.

¹ For patients with liver metastasis who begin treatment with Grade 2 AST or ALT, if AST or ALT increases by greater than or equal to 50% relative to baseline and lasts for at least 1 week then patients should be discontinued.

² Patients with intolerable or persistent Grade 2 drug-related AE may hold study medication at physician discretion. Permanently discontinue study drug for persistent Grade 2 adverse reactions for which treatment with study drug has been held, that do not recover to Grade 0-1 within 12 weeks of the last dose.

After discussion and approval from the Overall PI, dosing interruptions are permitted in the case

of medical / surgical events or logistical reasons not related to study therapy (e.g., elective surgery, unrelated medical events, patient vacation, and/or holidays). The reason for interruption should be documented in the patient's study record.

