	Participants who develop Grade 2 toxicity despite adequate premedication should be referred to allergy after discussion with the PI.	
Grades 3 or 4 Grade 3: Prolonged (i.e., not rapidly responsive to symptomatic medication and/or brief interruption of infusion); recurrence of symptoms following initial improvement; hospitalization indicated for other clinical sequelae (e.g., renal impairment, pulmonary infiltrates) Grade 4: Life-threatening; pressor or ventilatory support indicated	Stop Infusion. Additional appropriate medical therapy may include but is not limited to: IV fluids Antihistamines NSAIDS Acetaminophen Narcotics Oxygen Pressors Corticosteroids Epinephrine Increase monitoring of vital signs as medically indicated until the participant is deemed medically stable in the opinion of the investigator. Hospitalization may be indicated. Participant is permanently discontinued from further trial treatment administration.	No subsequent dosing

Appropriate resuscitation equipment should be available in the room and a physician readily available during the period of drug administration.

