Colitis (reported as ECI if \geq Grade 2 or any grade resulting in dose modification or use of systemic steroids to treat the AE)		
Intestinal Obstruction	Colitis	Colitis microscopic
Enterocolitis	Enterocolitis hemorrhagic	Gastrointestinal perforation
Necrotizing colitis	Diarrhea	
Endocrine (reported as ECI if \geq Grade 3 or \geq Grade 2 and resulting in dose modification or use of systemic steroids to treat the AE)		
Adrenal Insufficiency	Hyperthyroidism	Hypophysitis
Hypopituitarism	Hypothyroidism	Thyroid disorder
Thyroiditis	Hyperglycemia, if \geq Grade 3 and associated with ketosis or metabolic acidosis (DKA)	
Endocrine (reported as ECI)		
Type 1 diabetes mellitus (if new onset)		
Hematologic (reported as ECI if \geq Grade 3 or any grade resulting in dose modification or use of systemic steroids to treat the AE)		
Autoimmune hemolytic anemia	Aplastic anemia	Thrombotic Thrombocytopenic Purpura (TTP)
Idiopathic (or immune) Thrombocytopenia Purpura (ITP)	Disseminated Intravascular Coagulation (DIC)	Haemolytic Uraemic Syndrome (HUS)
Any Grade 4 anemia regardless of underlying mechanism		
Hepatic (reported as ECI if \geq Grade 2, or any grade resulting in dose modification or use of systemic steroids to treat the AE)		
Hepatitis	Autoimmune hepatitis	Transaminase elevations (ALT and/or AST)
Infusion Reactions (reported as ECI for any grade)		
Allergic reaction	Anaphylaxis	Cytokine release syndrome
Serum sickness	Infusion reactions	Infusion-like reactions
Neurologic (reported as ECI for any grade)		
Autoimmune neuropathy	Guillain-Barre syndrome	Demyelinating polyneuropathy
Myasthenic syndrome		
Ocular (report as ECI if \geq Grade 2 or any grade resulting in dose modification or use of systemic steroids to treat the AE)		
Uveitis	Iritis	
Renal (reported as ECI if \geq Grade 2)		
Nephritis	Nephritis autoimmune	Renal Failure
Renal failure acute	Creatinine elevations (report as ECI if \geq Grade 3 or any grade resulting in dose modification or use of systemic steroids to treat the AE)	
Skin (reported as ECI for any grade)		
Dermatitis exfoliative	Erythema multiforme	Stevens-Johnson syndrome
Toxic epidermal necrolysis		
Skin (reported as ECI if \geq Grade 3)		
Pruritus	Rash	Rash generalized
Rash maculo-papular		
Any rash considered clinically significant in the physician's judgment		
Other (reported as ECI for any grade)		
Myocarditis	Pancreatitis	Pericarditis
Any other Grade 3 event which is considered immune-related by the physician		

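### Section 5.3.2.6 allows pembrolizumab to be resumed by desensitization after an allergic reaction of any grade, while Tables 3 and 4 require permanent discontinuation at grade 3-4

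*Combined protocol and SAP*

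**What the plan says.** Section 5.3.2.6 is headed as dealing with infusion reactions. It first points the reader to section 6.3, then permits desensitization when a patient reacts allergically to the drug: "Patients who have an allergic reaction to pembrolizumab are allowed to continue on the protocol after a discussion with the Overall PI", with an allergy consultation as the second condition. It describes desensitization as giving the total planned dose over a longer time, guided by the investigator and an allergist. No CTCAE grade appears.

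Section 6 treats the same events by grade.

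- **Section 6.2:** "Pembrolizumab must be withheld for drug-related toxicities and severe or life-threatening AEs as per Table 3 below". The infusion-reaction row of Table 3 calls for permanent discontinuation at grades 3-4, and the note under the table adds: "Permanently discontinue for any severe or Grade 3 drug-related AE that recurs or any life-threatening event".
- **Section 6.3.1, Table 4, grade 3 or 4:** "Participant is permanently discontinued from further trial treatment administration". The premedication column for that row rules out any later dose.
- **Section 6.3.1, Table 4, grade 2:** "Participants who develop Grade 2 toxicity despite adequate premedication should be referred to allergy after discussion with the PI".

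Appendix B (Table 1 and section 3.11) places allergic reaction and anaphylaxis in its infusion-reaction category.

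**The concern.** A permission without a grade limit sits in the administration section, and a grade-specific prohibition sits in the dose-modification section. A clinician who works from 5.3.2.6 could, after speaking to the Overall PI and an allergist, give the full dose again to a patient whose first reaction was severe or life-threatening. The tables forbid this. What is at stake is re-exposure of such a patient on the strength of the protocol's own wording.

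The placement adds to the problem. The nursing education sheet sends infusion staff to sections 5.3.1 and 5.3.2 for administration and separately to section 6 for dose modification, so the permission is in a section that staff are told to use.

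**Working it through.** The point is mainly textual, and the plan states no figure to reproduce. The provisions compare as follows.

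| Reaction to pembrolizumab | Section 5.3.2.6, read literally | Table 3 and its note | Table 4 |
|---|---|---|---|
| Grade 1 | May continue, with PI discussion and allergy consultation | No infusion-reaction rule | Monitor; no premedication |
| Grade 2 | Same | No infusion-reaction rule | Interrupt, treat, may restart at half rate; referral to allergy after PI discussion if it occurs despite premedication |
| Grade 3 | Same | Permanent discontinuation | Permanent discontinuation, no later dose |
| Grade 4 | Same | Permanent discontinuation; also caught by the note on life-threatening events | Permanent discontinuation, no later dose |

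1. **Do the terms cover the same events?** The permission speaks of allergic reactions and the tables of infusion reactions. The permission stands under an infusion-reaction heading, and Appendix B files allergic reaction and anaphylaxis under infusion reactions. The categories overlap, so the difference in terms does not separate the rules.
2. **Does any text rank them?** The pointer to section 6.3 comes before the permission, but it neither makes the permission subject to Table 4 nor limits its grade. Section 6 does not mention desensitization or 5.3.2.6. Appendix B (section 1) sends dose-modification questions back to the protocol's own language, so it does not settle which protocol section prevails.
3. **Is the same wording harmless elsewhere?** Section 5.3.1.7 gives nearly the same permission for PLD. The PLD tables in section 6.1 cover hand-foot syndrome, stomatitis, neutropenia and thrombocytopenia and have no infusion-reaction row, so the ungraded wording contradicts none of them. For pembrolizumab it meets an explicit grade 3-4 rule.
4. **Where do the rows part?** Only at grades 3 and 4. At grades 1 and 2 both sections can be followed together.

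The difference for one affected patient can be bounded. Section 5.6 ends pembrolizumab once: "Participant has completed 35 treatments (approximately 2 years) with pembrolizumab". With a grade 3-4 reaction at treatment *k*:

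- Literal 5.3.2.6: at most 35 − *k* further doses. For *k* = 1, 35 − 1 = 34; for *k* = 2, 35 − 2 = 33.
- Tables 3 and 4: 0 further doses at any *k*.

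The number of affected patients among the 26 cannot be derived, because the documents give no rate of grade 3-4 pembrolizumab reactions. None is assumed here.

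**The case against.** The best defence is that the protocol already resolves this for a careful reader. Section 5.3.2.6 cites section 6.3 before it mentions desensitization, and Table 4 in that section rules out further dosing at grade 3-4. Section 6.2 uses mandatory language. The drafting also shows where the line was meant to fall: for grade 2 despite premedication, Appendix B discontinues the patient, whereas Table 4 substitutes referral to allergy after PI discussion, which are the two conditions in 5.3.2.6. The grade 3-4 row was left as discontinuation. Re-dosing would also need the agreement of the Overall PI, who is the study sponsor, and the guidance of an allergist. Infusion reactions of any grade must be reported to the drug supplier within 24 hours.

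Much of this stands. The harmonised reading is probably the intended one, nothing shows that re-dosing after a grade 3-4 reaction was planned, and discontinuing such a patient complies with every section. The safeguards lower the chance of harm. The 35 − *k* figure is only a ceiling: it measures neither risk nor likelihood, and a recurrent severe or grade 3 drug-related event would itself end treatment under the note to Table 3.

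What does not stand is the claim that the limit is already in place. It has to be inferred from other sections. A reader could instead take 5.3.2.6 as a specific exception to tables whose titles call them guidelines. PI discussion and allergy consultation are the conditions for using the permission; they do not set a grade above which it ceases to apply.

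**Conclusion.** The concern holds. As written, 5.3.2.6 permits continued pembrolizumab after an allergic reaction of any grade, and for grade 3-4 that conflicts with Table 3, its note and Table 4. It is an inconsistency of wording, not a pair of opposite commands, since stopping treatment satisfies all the provisions.

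Its reach is narrow: grade 3-4 allergic or infusion reactions to pembrolizumab, in a number of patients that may be zero. It should still be corrected, because the conduct literally allowed is re-exposure after a reaction that may have been life-threatening. The conclusion rests on a literal reading of 5.3.2.6 and on the overlap between allergic and infusion reactions shown by that section's heading and Appendix B. No endpoint or element of the statistical design is affected.

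**What to change.** Amend 5.3.2.6 to say that desensitization and continued pembrolizumab apply only to grade 1-2 allergic or infusion reactions, including grade 2 despite premedication as in Table 4, and that grade 3-4 reactions lead to permanent discontinuation under Tables 3 and 4.

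The cost is one clarifying sentence in a protocol amendment. It withdraws nothing that the tables allow and leaves the sample size, visit schedule and analysis unchanged. The Appendix B grade 2 row can stay as it is, because that appendix already defers to the protocol on dose modification.

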5.3.2.7 Order of Administration

If PLD and pembrolizumab infusions do occur on the same day, pembrolizumab should be given first, followed by PLD.

5.4 Definition of Dose-Limiting Toxicity (DLT)

Toxicities that are considered DLT toxicities that occur during the first 4 weeks of treatment will be monitored; if 2 out of the first 6 patients develop a DLT, the dose of PLD will be reduced to 30 mg/m².

Definition of DLT: Dose limiting toxicity (DLT) refers to both non-hematologic and hematologic toxicities deemed by the treating physician to be related to study treatment experienced during the first cycle (i.e. first 4 weeks) of treatment.

A DLT will be defined as any of the following, occurring during Cycle 1:

1. Non-Hematologic Toxicity

Any Grade 3 or 4 event, excluding:

- Fatigue
- Grade 3 nausea and/or vomiting controlled with supportive measures within 24 hours,
- Grade 3 constipation controlled with supportive measures within 24 hours,
- Grade 3 diarrhea controlled with supportive measures within 24 hours,
- Grade 3 hypophosphatemia,
- Grade 3 hyponatremia,
- Grade 3 hypomagnesemia
- Grade 3 rash that does not resolve to grade 2 or grade 1 within \leq 5 days

2. Hematologic Toxicity

- Grade 4 neutropenia of > 7 day's duration
- Febrile neutropenia (a disorder characterized by an ANC $< 1000/\text{mm}^3$ and a single temperature of $> 38.3^\circ\text{C}$ (101°F) or a sustained temperature of $\geq 38^\circ\text{C}$ (100.4°F) for more than one hour.
- Dose delay of greater than 3 weeks (21 days) due to failure to recover counts.
- Grade 4 thrombocytopenia or bleeding associated with grade 3 thrombocytopenia.
Any other hematologic toxicities of Grade 4
Requirement for repeated blood transfusion within 4-6 weeks

3. Any study treatment related death.

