13. STATISTICAL CONSIDERATIONS

This is a non-randomized single-arm phase II study designed to evaluate the safety and efficacy of pegylated liposomal doxorubicin (PLD) and pembrolizumab for the treatment of platinum resistant recurrent ovarian, fallopian tube or peritoneal cancer. A six patient safety lead will be performed of these 2 drugs given in combination at their recommended phase II doses, respectively. If 2 out of the first 6 patients develop a DLT, the dose of PLD will be reduced to 30 mg/m². If no more than 1 patient of the first 6 patients has evidence of dose limiting toxicities, the dose level will be considered the maximum tolerated dose (MTD), an additional 20 patients will be enrolled to complete the phase II study.

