13.1 Study Design/Endpoints

Primary safety endpoint:

- Dose limiting toxicity that occur during the first 4 weeks of treatment, as defined in Section 5.4

For the safety run-in using cohorts of 6 patients at any dose level, the following table gives the probability of continuing to the phase II portion of the study under varying true rates of dose-limiting toxicity.

	Acceptable dosage using 6 subjects						
True DLT rate	0.1	0.2	0.3	0.4	0.5	0.6	0.7
Probability	89%	66%	42%	23%	11%	4%	1%

Primary efficacy endpoint:

- Clinical benefit rate (CR + PR + SD \geq 24 weeks)

Secondary endpoints include:

- Toxicity by CTCAE version 4.0
- Objective response by RECIST 1.1.
- Progression-free survival
- Overall survival
- Time to progression
- Duration of response

Patients who withdraw study consent before receiving any study treatment will be replaced.

Patients who are receive study treatment, but who go off-treatment or off-study in cycle 1 and are not evaluable for DLT will be replaced for the safety run-in, but will be considered as non-responders in the final efficacy analysis.

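### The Grade 3 rash item among the DLT exclusions in Section 5.4 is inverted: it excuses a persistent rash and counts one that clears quickly

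*Combined protocol and SAP*

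**What the plan says.** Section 5.4 limits DLTs to toxicities "deemed by the treating physician to be related to study treatment experienced during the first cycle (i.e. first 4 weeks) of treatment". For non-hematologic toxicity the rule is "Any Grade 3 or 4 event, excluding", followed by a list of events that do not count. Three items on that list carry a time condition of 24 hours: nausea and/or vomiting, constipation and diarrhea. The diarrhea item is typical: "Grade 3 diarrhea controlled with supportive measures within 24 hours". The last item is "Grade 3 rash that does not resolve to grade 2 or grade 1 within" 5 days or less.

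Section 13.1 defines the primary safety endpoint as "Dose limiting toxicity that occur during the first 4 weeks of treatment, as defined in Section 5.4". Section 13 gives the rule for going on: "If no more than 1 patient of the first 6 patients has evidence of dose limiting toxicities", the dose is taken as the MTD and 20 more patients are enrolled. Section 5.4 gives the other branch: "if 2 out of the first 6 patients develop a DLT, the dose of PLD will be reduced to 30 mg/m²".

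**The concern.** An item on an exclusion list describes what is forgiven. The nausea/vomiting, constipation and diarrhea items forgive a Grade 3 event only if it is brought under control quickly. The rash item forgives the event only if it fails to improve quickly, so the worse course is excused and the milder one is counted. The wording fits a DLT criterion, but it stands in a list of exceptions, which points to a drafting slip.

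What is at stake is the primary safety endpoint and the dose decision that rests on it. With six patients and a boundary between one and two DLTs, reclassifying a single patient can change the PLD dose given to everyone enrolled afterwards. Rash is not a remote possibility: Section 7.1 lists it among the most common PLD reactions and among the pembrolizumab reactions reported in at least 20% of patients, though without a breakdown by grade.

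**Working it through.** **Step 1. Classification under each reading.** The patient has a treatment-related rash in cycle 1 and no other DLT.

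| Event | As written | Negation removed |
|---|---|---|
| Grade 3 rash, down to grade 2 or lower within 5 days | DLT | Not a DLT |
| Grade 3 rash persisting beyond 5 days | Not a DLT | DLT |
| Grade 4 rash | DLT | DLT |

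A rash judged unrelated to treatment is not a DLT under either reading. No other section states a different rash rule for DLTs; the nursing education sheet simply refers back to Section 5.4.

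**Step 2. The plan's own table.** The probability of continuing is P(X ≤ 1) with X ~ Bin(6, p), that is (1−p)⁶ + 6p(1−p)⁵. At p = 0.1 to 0.7 this gives 88.6, 65.5, 42.0, 23.3, 10.9, 4.1 and 1.1%. All seven agree with Section 13.1 (89, 66, 42, 23, 11, 4 and 1%). The table is indexed by the true DLT rate, so it is correct whichever way the rash item reads. What the wording changes is which patients count as DLTs, and hence which p applies.

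**Step 3. Effect on the probability of continuing.** The documents give no Grade 3 rash rate, so every rate here is an assumption. Let o be the rate of other DLTs. Among patients without another DLT, let r be the rate of persistent Grade 3 rash and q the rate of quickly resolving Grade 3 rash, both independent of other DLTs.

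- As written: p = 1 − (1−o)(1−q)
- Corrected: p = 1 − (1−o)(1−r)

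For example, with o = 0.10, r = 0.05 and q = 0, p is 0.100 as written and 1 − 0.90 × 0.95 = 0.145 corrected. With q = 0:

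| o | r | p as written | P(continue) as written | p corrected | P(continue) corrected |
|---|---|---|---|---|---|
| 0.10 | 0.005 | 0.100 | 88.6% | 0.1045 | 87.7% |
| 0.10 | 0.01 | 0.100 | 88.6% | 0.109 | 86.8% |
| 0.10 | 0.02 | 0.100 | 88.6% | 0.118 | 84.9% |
| 0.10 | 0.05 | 0.100 | 88.6% | 0.145 | 78.8% |
| 0.10 | 0.10 | 0.100 | 88.6% | 0.190 | 68.0% |
| 0.20 | 0.02 | 0.200 | 65.5% | 0.216 | 61.6% |
| 0.20 | 0.05 | 0.200 | 65.5% | 0.240 | 55.8% |
| 0.20 | 0.10 | 0.200 | 65.5% | 0.280 | 46.4% |

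If only quickly resolving rash occurs (r = 0, with q at the same values), the two P(continue) columns change places.

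**Step 4. Wrong decisions.** When r = q, P(continue) is the same under both readings, but individual decisions can still be wrong. Each patient falls into one of four classes: other DLT (o), persistent rash only ((1−o)r), quickly resolving rash only ((1−o)q), or none. Summing the multinomial probabilities for n = 6 over outcomes where the two readings disagree, with o = 0.10:

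| r | q | Continue wrongly | Stop wrongly |
|---|---|---|---|
| 0.005 | 0.005 | 0.9% | 0.9% |
| 0.01 | 0.01 | 1.7% | 1.7% |
| 0.02 | 0.02 | 3.4% | 3.4% |
| 0.05 | 0.05 | 8.2% | 8.2% |
| 0.05 | 0 | 9.8% | 0% |
| 0 | 0.05 | 0% | 9.8% |

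**The case against.** The strongest objection concerns how often this bites. It needs one of six patients to have a related Grade 3 rash in cycle 1, no other DLT, and a total that crosses from one to two or back. It also needs the text to be applied literally, although an investigator may well see what was meant; the percentages above assume literal application every time. The scope is narrow as well: hand-foot syndrome is listed separately from rash, and at Grade 3 or 4 it still counts, as do Grade 3 or 4 stomatitis and any Grade 4 rash. The larger shifts assume 5 to 10% persistent rash and none that clears quickly; at 1% or less the effect is small. Section 13.3 requires a safety review before further enrollment. The patient's own care does not depend on the label, since the pembrolizumab guidance in Appendix B holds the drug for Grade 3 skin events. Finally, the intended rule is inferred: the documents do not state it, and the line might once have stood outside the exclusion list as a criterion of its own.

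Much of this stands as a limit on frequency and size. It does not rescue the rule. The safety review applies the same definition, so it does not correct it. If the outcome depends on someone guessing the intent, the primary safety endpoint depends on who adjudicates, and the right answer departs from the approved text. Nothing in the current text shows the rash line outside the exclusion list.

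**Conclusion.** The concern holds. Followed literally, Section 5.4 misclassifies any treatment-related cycle 1 Grade 3 rash in a lead-in patient with no other DLT, in either direction. That the opposite was intended is an inference, but the nausea/vomiting, constipation and diarrhea items all support it and the plan gives no reason for excusing only the persistent rash.

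The size cannot be fixed from the documents. Under the assumed rates with 10% other DLTs, one-sided persistent rash of 0.5 to 10% overstates the probability of continuing by about 1 to 21 percentage points (88.6% against 87.7% down to 68.0%). With no Grade 3 rash among the six there is no effect. The one-of-six threshold and the Section 13.1 table are correct, and the efficacy rule of 10 of 26 does not depend on this item. Because a primary endpoint and a dose decision rest on the line, it should be corrected despite the low expected frequency.

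**What to change.** Replace the item in Section 5.4 with: *Grade 3 rash resolving to grade 2 or lower within 5 days*. It then works like the other time-limited exclusions: only a quickly resolving Grade 3 rash is excused, while a Grade 3 rash lasting beyond 5 days and any Grade 4 rash count as DLTs.

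If any lead-in patient has had a Grade 3 rash, re-adjudicate it under the corrected wording before the six-patient decision is relied on. If none has, nothing further is needed.

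The cost is a one-line protocol correction plus that conditional re-adjudication. Sample size, decision threshold and probability table stay as they are.
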